- In the case of PD, treatment may continue past the initial determination of PD or confirmed PD if the participant's performance status has remained at least stable, and if in the opinion of the Investigator, the participant will benefit from continued treatment and if other criteria are fulfilled as outlined in the protocol.
- In the case of stable disease, partial response, or complete response, treatment should be continued until the end of 24 months. If the Investigator believes that a participant will benefit from treatment beyond 24 months, it may be permissible after discussion with the Medical Monitor and the Sponsor Medical Responsible.
- Safety Follow-up will continue until 12 weeks after the last dose of bintrafusp alfa. The 12-week Safety Follow-up is allowed to be conducted via telephone calls or patient chart reviews unless there is medical necessity requiring a clinical visit.
- Long-term Follow-up for progression and survival should be performed every 12 weeks after the Safety Follow-up according to the Schedule of Activities. Long-term Follow-up should be performed by patient chart reviews or telephone calls unless a clinical visit is indicated.

Number of Participants:

The planned total sample size is 29 female participants to address the primary and other efficacy objectives, safety assessments, and evaluation of the clinical utility of the RT-PCR-based assay for HMGA2. CCI

Assuming a true objective response rate of 30%, the probability to observe a lower bound of the exact 95% confidence interval above 10% (the benchmark for clinically non-relevant effect) would be 81% when analyzing 29 participants.

Study Intervention Groups and Duration:

[figure not shown]
The planned maximum study duration for a participant is estimated to be up to 24 months (in certain instances, this duration may be lengthened if it is in the best interest of the participant to continue further treatment). This includes a 28-day Screening period (decision will be made in this period for participants' study inclusion if all eligibility criteria are met); a treatment duration until confirmed PD, unacceptable toxicity, study withdrawal or death occurs, a 28-day Safety Follow-up Visit, a 12-week Safety Follow-up phone call after the last dose of bintrafusp alfa, and a Long-term Follow-up (performed every 12 weeks after the Safety Follow-up).

Involvement of Special Committee(s): Yes

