In an exploratory analysis of RNAseq data from tumor samples in the TNBC participants, high expression of HMGA2 was associated with response to bintrafusp alfa ([Figure 2](#)). A total of 5 TNBC participants in the cohort experienced disease control and had high HMGA2 expression; of these participants, 4 had a partial response (PR) and 1 had SD. One of these participants with a PR had high levels of HMGA2 expression, but low quality RNAseq data, precluding the result from being included in the formal biomarker assessment. However, even excluding that 1 participant, there was a 32.0-fold higher mean expression of HMGA2 in the participants who experienced disease control compared with those who had progressive disease (PD). Using an HMGA2 cutoff defining high expression as the lowest HMGA2 expression in a participant experiencing PR, there were 3 additional participants in the cohort of 33 participants considered to have high HMGA2 (total 8/33, 24%). Of these 3 additional participants, 2 had PD and 1 was non-evaluable as a best response. In summary, 8 participants had high levels of HMGA2 expression, 5 of which experienced disease control, including 4 PRs (ORR in HMGA2 50%, disease control rate 62.5%). As per The Cancer Genome Atlas, approximately 12% of patients with TNBC are projected to have high HMGA2 expression using a comparable cutoff.

HMGA2 is downstream of the TGF- β signaling pathway and is known to be a key regulator of epithelial mesenchymal transformation (Thuault 2006). Classically, HMGA2 is associated with poor prognosis, including in breast cancer (Wu 2016). The clinical activity observed in the TNBC cohort in Study EMR200647-001 suggests that participants expressing high levels of HMGA2 might particularly benefit from treatment with a bifunctional molecule which targets TGF- β and PD-L1, such as bintrafusp alfa (Locke 2019a).

Based on the biological rationale and promising clinical activity of bintrafusp alfa in TNBC and manageable safety profile in participants with various cancer types (refer to the bintrafusp alfa IB), this study is designed to further investigate bintrafusp alfa in participants with TNBC expressing high levels of HMGA2.

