4.1 Overall Design

This is a Phase II, multicenter, single-arm, open label study to evaluate bintrafusp alfa monotherapy in participants with TNBC who express high levels of HMGA2 as determined by a centralized reverse transcriptase-polymerase chain reaction (RT-PCR) test with predefined cutoff. Participants must have progressed during or after first-line of chemotherapy.

The primary objective is to evaluate the clinical efficacy of bintrafusp alfa based on the ORR as assessed by an IRC. The key secondary objectives are duration of response (DOR), durable response rate (DRR), progression-free survival (PFS), OS, and safety. Tumor response evaluations based on Response Evaluation Criteria in Solid Tumors Version 1.1 (RECIST 1.1) ([Eisenhauer 2009](#)) will be performed every 8 weeks until 12 months after the first administration of bintrafusp alfa and then every 12 weeks until confirmed disease progression, unacceptable toxicity, or occurrence of any criterion for withdrawal from the study.

The study plans to enroll approximately 29 eligible participants globally with competitive enrollment.

The study includes:

- Prescreening (a Prescreening informed consent form [ICF] will be used for HMGA2 biomarker analysis and collection of baseline clinical history). Positive HMGA2 test results on tumor tissue is required to enter formal study Screening (see [Table 1](#)).
- Up to 28-day Screening period.
- Treatment with bintrafusp alfa at a dose of 1200 mg intravenously once every 2 weeks until confirmed PD, unacceptable toxicity, study withdrawal, or death.
- In the case of PD, treatment may continue past the initial determination of PD or confirmed PD, if the participant's performance status (PS) has remained at least stable, and if in the opinion of the Investigator, the participant will benefit from continued treatment and if other criteria are fulfilled as outlined in the protocol (see [Section 7.1.3](#)).
- In the case of SD, PR, or complete response (CR), treatment should be continued until the end of 24 months. If the Investigator believes that a participant will benefit from treatment beyond 24 months, it may be permissible after discussion with the Medical Monitor and the Sponsor Medical Responsible.
- Safety Follow-up will continue until 12 weeks after the last dose of bintrafusp alfa. The 12-week Safety Follow-up is allowed to be conducted via telephone calls or patient chart reviews, unless there is medical necessity requiring a clinical visit.

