Continuous (non-PK) variables will be summarized using descriptive statistics, i.e., the number of participants with non-missing values (n), arithmetic mean (Mean), standard deviation (StD), median (Med), 25th percentile (Q1) and 75th percentile (Q3), minimum (Min), and maximum (Max).

Qualitative variables will be summarized by frequency counts and percentages. Unless otherwise stated the calculation of proportions will be based on the number of participants of the analysis set of interest. Therefore, counts of missing observations will be included in the denominator and presented as a separate category.

Descriptive statistics by nominal visit or time point, will include only data from scheduled visits, unless stated otherwise. Unscheduled visits will be included in the derivation of baseline or worst on-treatment values.

The overall significance level is 2.5% one-sided. If confidence intervals (CIs) are to be calculated, these will be two-sided with a confidence probability of 95%, unless otherwise specified in this IAP.

In order to provide overall estimates of treatment effects, data will be pooled across sites. The “site” factor will not be considered in statistical models or for subgroup analyses due to the high number of participating sites in contrast to the anticipated small number of participants treated at each site.

Pharmacokinetics (PK) variables (concentrations and parameters) will also be summarized as described in Section 16.1. Refer also to Section 16.1 for PK data handling/analysis details.

All statistical analyses will be performed using SAS® Software Version 9.4 or higher in the SAS Grid environment (Statistical Analysis System, SAS-Institute, Cary NC, USA). The computer program Phoenix® WinNonlin® Version 8.0, or higher (Certara, L.P., Princeton, New Jersey, USA) could be used for PK data.

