10.1 Disposition of Participants and Discontinuations

The number and percentage of participants in each of the below disposition categories will be presented based on the data collected in the eCRF. Percentages will be presented with respect to the number of treated participants.

- Total number of prescreened participants
- Number of participants who did not continue beyond prescreening (overall and by reason)
- Total number of participants screened (i.e. participants who gave informed consent)
- Number of re-screened participants
- Number of participants who discontinued from the study prior to treatment overall and grouped by the main reason (e.g. the failed specific inclusion or exclusion criteria, progressive disease, adverse event, lost to follow-up, death, withdrawal of consent and other)
- Number of participants who received at least one dose of study intervention (FAS/SAF analysis set)

The end of treatment status will be summarized by:

- Number and percentage of participants with treatment ongoing at the data cut-off date
- Number and percentage of participants off study treatment, grouped by main reason (treatment completed as per protocol, progressive disease, death, adverse event, lost to follow-up, protocol non-compliance, withdrew consent, other)

With regards to treatment reinitiation status, it will be summarized by:

- Number and percentage of participants who reinitiated the study treatment
- Number and percentage of participants with treatment ongoing after reinitiation
- Number and percentage of participants who discontinued treatment after reinitiation

The end of study status will be summarized by:

- Number and percentage of participants with study ongoing at cut-off date (including participants with treatment ongoing and participants who are off treatment and in follow-up)
- Number and percentage of participants who completed/discontinued the study participation, with the associated main primary reason (study completed according to protocol, adverse event, lost to follow-up, protocol non-compliance, death, withdrew consent, other)

In addition, the number of participants screened, and enrolled in each analysis population defined in Section 8.1 will be summarized, overall and by region (North America and Europe), country within region and site.

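### SAP 10.1 sets treated participants as the denominator for every disposition row, so the prescreening, screening and pre-treatment percentages are not valid proportions

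*SAP*

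**What the plan says.** SAP 10.1 opens with "The number and percentage of participants in each of the below disposition categories will be presented based on the data collected in the eCRF" and follows at once with "Percentages will be presented with respect to the number of treated participants". The rows directly below start with "Total number of prescreened participants" and "Number of participants who did not continue beyond prescreening (overall and by reason"). Then come total screened, re-screened, discontinued before treatment by main reason, and those who received at least one dose. Separate blocks for end of treatment, reinitiation and end of study come after these.

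Two other parts of the SAP bear on the denominator. Section 9 gives the general rule: "Unless otherwise stated the calculation of proportions will be based on the number of participants of the analysis set of interest". Section 8.1 defines prescreening (PRESCR) and screening (SCR) sets, and Table 2 assigns disposition to those two sets, not to FAS or SAF.

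Protocol 4.1 sets the gate between the stages: "Positive HMGA2 test results on tumor tissue is required to enter formal study Screening". SAP 4.1, added in version 2.0 after the decision to stop the study early, cancels the biomarker analyses and allows listings to replace summary tables where judged appropriate.

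**The concern.** A percentage describes a group only if the group is part of the denominator. Total prescreened and total screened contain the treated participants. Those stopped at prescreening and those discontinued before treatment share no member with them. Re-screened participants may or may not have gone on to treatment. Dividing any of these by the number treated gives a ratio, not a proportion.

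What is at stake is how attrition at the biomarker gate is reported. The protocol synopsis gives "evaluation of the clinical utility of the RT-PCR-based assay for HMGA2" as one purpose of the sample size. How many patients are lost at prescreening, and why, is basic descriptive information about a trial selected by that assay. A percentage column built on the treated would misstate it.

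**Working it through.** **The plan's own figures.** The documents state no disposition percentage. The nearest figure is the basis for 29 treated participants. With n = 29, the smallest count whose exact 95% lower bound exceeds 10% is 7 (7/29 gives 10.3%; 6/29 gives 8.0%). At a true ORR of 30%, P(7 or more responses) = 0.812, which agrees with the stated 81%. The Phase I share of HMGA2-high tumours, 8/33 = 24.2%, also reproduces.

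**Step 1: without any prevalence.** Every treated participant passed through prescreening and screening. So prescreened/treated ≥ 100% and screened/treated ≥ 100%. Each exceeds 100% as soon as one person fails at or after that stage.

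**Step 2: size of the distortion.** Inputs:
- T = 29 planned treated (protocol synopsis).
- p = share HMGA2-high. Protocol 2.2 gives 24% in the Phase I cohort and a projection: "approximately 12% of patients with TNBC are projected to have high HMGA2 expression using a comparable cutoff".
- s = share of HMGA2-high participants who are never treated. The documents give no value. Take s = 0, the most favourable case.

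Formulas: prescreened N = T/((1 − s)p); stopped at prescreening F = N(1 − p). With s = 0, and N rounded up to whole participants:

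| p | N | F = N − 29 | N/29 (SAP 10.1) | F/29 (SAP 10.1) | F/N (of prescreened) |
|---|---|---|---|---|---|
| 24% | 29/0.24 → 121 | 92 | 417% | 317% | 76% |
| 12% | 29/0.12 → 242 | 213 | 834% | 734% | 88% |

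Without rounding N, the 12% row reads 833% and 733%.

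**Step 3: sensitivity.** If s is assumed to be 20% to 30% (an illustration, not a documented value), failures read 396% to 452% of treated at p = 24% and 917% to 1048% at p = 12%. Total screened reads 125% to 143%. The share of prescreened stays at 76% and 88%.

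**Step 4: dependence on trial size.** With s = 0 and no rounding, F/T = (1 − p)/p. T cancels, so stopping with few treated participants does not remove the problem. The failure row exceeds 100% whenever p is below 50%.

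**The case against.** The strongest reply is that the intended reading is visible in the layout. The pre-treatment bullets ask only for a number, while the end-of-treatment, reinitiation and end-of-study bullets ask for a number and a percentage. The treated denominator is right for exactly those later rows. That is a fair account of what was probably meant. It does not settle the matter, because the opening sentence of 10.1 expressly promises percentages for each category below it. The text is at best ambiguous.

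Second, the table may never be produced, since SAP 4.1 allows listings instead. This stands as a limit on impact. It is discretionary, however, and the version 2.0 change log shows no revision of 10.1.

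Third, the sizes above are inferences. The 24% comes from an RNAseq cutoff set after the fact at the lowest-expressing responder, and the 12% is a projection from an outside database. Neither is the trial's RT-PCR cutoff. This also stands, but Step 1 needs no prevalence.

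A reader might go further and infer that no valid HMGA2-high rate will be reported. The documents do not support that. The number prescreened and the numbers stopped by reason are reported as counts, so a rate could be derived if the reasons separate HMGA2 not high from not evaluable and other causes. Large parts of the biomarker text in both documents are redacted, so a rate planned there cannot be excluded.

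A reader might also say that 10.1 overrides a correct default. That is too loose. Table 2 names PRESCR and SCR jointly, so the default does not single out one denominator, and neither set suits the treatment-status rows. The fault lies in the scope of the 10.1 sentence.

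**Conclusion.** The point holds as a minor error of reporting specification. Taken literally, SAP 10.1 gives invalid percentages for five pre-treatment rows, and the prescreened and screened totals cannot fall below 100%. On the protocol's background prevalence, and assuming every HMGA2-high participant is treated, prescreening failures would be shown as roughly 317% to 734% instead of 76% to 88%. Further loss after the HMGA2 test would make the shown figures larger. The underlying counts are right. The primary ORR analysis, the sample size and alpha do not depend on this sentence.

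**What to change.** Replace the denominator sentence in SAP 10.1 with:

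*Percentages use the number prescreened (PRESCR) for prescreening rows, the number screened (SCR) for screening and pre-treatment discontinuation rows, and the number treated for end-of-treatment, reinitiation and end-of-study rows.*

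Apply the same denominators to any percentage quoted in the abbreviated CSR if only listings are produced under SAP 4.1. Optionally, show HMGA2 not high and not evaluable as separate prescreening reasons, provided the eCRF holds them; the visible text does not confirm that it does.

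The cost is one sentence and one table shell. Both analysis sets are already defined in SAP 8.1. The core change needs no new data.

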10.2 Protocol Deviations/Exclusion from Analysis Populations

10.2.1 Important Protocol Deviations

Analysis Set: FAS

Important protocol deviations (IPDs) are protocol deviations that might significantly affect the completeness, accuracy, and/or reliability of the study data or that might significantly affect a participant's rights, safety, or well-being.

A full list of potential protocol deviations including definition and categorization is maintained in [Appendix 1 – Definition of Important Protocol Deviations](#).

Important protocol deviations will be summarized for:

- Deviations from the inclusion and exclusion criteria
- Deviations post inclusion

A frequency table for IPDs, separated for such pre-/post inclusion deviations, as well as a listing will be provided. The listing will include: participant identifier, type of protocol deviation (e.g. inclusion/exclusion), category of the deviation (code assigned), and a description of the deviation and will be sorted by participant identifier.

COVID-related protocol deviations will contain the wording “COVID”, ”COVID-19”, ”SARS-COV-2” or similar at the beginning of the PD description in order to easily identify them.

Considerations for Pharmacokinetics

Protocol deviations or events will be reviewed by the study pharmacokineticist and biostatistician to identify deviations or events which have the potential to affect the PK results. Deviations, changes to the procedures, or events resulting in non-evaluable PK results, and thus exclusion from PK summaries, will be documented as reasons for exclusion from these summaries, and will be described within the CSR body text. These changes or events will include any circumstances that will alter the evaluation of the PK. Examples of important protocol deviations or important events for PK in terms of this study may include, but may not be limited to the following:

- Dose delayed outside the allowed window
- Actual dosing time not recorded
- Dose change, missed dose, or incomplete/inaccurate dose
- Pre-dose sample collected after the actual start of infusion
- End-of-infusion sample collected before the actual end of infusion
- Documented sample processing errors or analytical errors that may lead to inaccurate bioanalytical results

For the above important protocol deviations or important events for PK, the relevant PK data will be excluded from summaries based on the PKAS. Other changes to the procedures or events which do not impact the quality of the PK data will not be considered important protocol deviations for PK. Common examples of minor (non-important) protocol deviations are a missed sample or minor deviations from sample collection times/windows.

Refer to section [16.1](#) for more details of protocol deviations and handling relevant to PK.

10.2.2 Reasons Leading to the Exclusion from an Analysis Population

A frequency table per listing of excluded PK data and reasons of for exclusion from summaries/analyses based on the PKAS as well as a listing will be provided.

11

Demographics and Other Baseline Characteristics

Analysis Set: FAS

11.1

Demographics

Demographic characteristics and physical measurements will be summarized descriptively using the following information from the Screening/Baseline Visit eCRF pages.

The following demographic characteristics will be included:

- Sex: male, female
- Ethnicity: Hispanic or Latino/Not Hispanic or Latino, Japanese/Not Japanese
- Race:
 - For participants reporting one race only: White, Black or African American, Asian, American Indian or Alaska Native, Native Hawaiian or other Pacific Islander, Not collected at the site, Other.
 - For participants reporting several races, all combinations will be reported under ‘More than one race’ category.
- Age (years)
- Age categories:
 - < 65 years: 18-49 and 50-64 years
 - ≥ 65 years: 65-74, 75-84 and ≥85 years
- Pooled Geographic Region:
 - North America
 - Europe

Demographic characteristics including participant identifier, sex, race (including all reported races in case of “multiple” races, and details in case of “other” race), ethnicity, geographic region, age (years and category), height, weight and body mass index (BMI) at baseline will be presented in a listing and sorted by participant ID.

Specifications for computation:

- Age [years]: (date of given informed consent - date of birth + 1) / 365.25
 - In case of missing or partial dates see age imputation rules in [Table 3](#).
 - The integer part of the calculated age will be used for reporting purposes.
- Site codes will be used for the determination of the participant’s geographic region.
- BMI (kg/m^2) = weight (kg)/[height (m)] 2 .

11.2

Medical History

The medical history will be summarized from the “Medical History Details” eCRF page, using the most recent Medical Dictionary for Regulatory Activities (MedDRA) version at time of database lock, preferred term (PT) as event category and system organ class (SOC) body term as Body System category.

Medical history will be displayed in terms of frequency tables: ordered by primary SOC and PT in alphabetical order. Each participant will be counted only once within each PT or SOC. Categories for human immunodeficiency virus (HIV) infection, multi-drug resistance preventing effective antiretroviral therapy, multi-drug resistance not preventing effective antiretroviral therapy and acquired immune deficiency syndrome (AIDS) defining opportunistic infection will be also displayed in a separate table.

Listing of medical history including participant identifier, age, sex, race, PT, reported medical history term, start/end dates, related study condition, ongoing at screening and toxicity grade (when medical history is ongoing) will be presented. This listing will be sorted by participant identifier, start date, end date and PT.

11.3

Other Baseline Characteristics

11.3.1

Disease History

Information on disease characteristics collected on the “Disease History” eCRF page will be summarized as follows:

- Histological diagnosis: lobular, ductal, paget, other
- Time since initial cancer diagnosis (months)
- Time since documented, inoperable or metastatic disease diagnosis (months)
- Time since last progression of disease prior to study entry (months)
- Tumor Node Metastasis (TNM) classification at initial diagnosis: each T, N, M category will be described (TX, T0, N1, etc.)

Listing will also be provided with the following information: participant identifier, age, sex, race, histological diagnosis, date of initial cancer diagnosis (months), date of documented, inoperable or metastatic disease (months), date of last progression of disease prior to study entry (months), and TNM classification at initial diagnosis.

A second listing will be provided containing the molecular abnormalities information, including: participant identifier, age, sex, race, molecular abnormality (estrogen receptor, progesterone receptor, human epidermal growth factor 2, and other molecular abnormality), date of sample (months before first bintrafusp alfa administration), result and percentage. For other molecular abnormalities, tumor genomic marker and codon and kit used for mutation assessment will also be displayed. This listing will be sorted by participant ID.

